5.5. Multiple Comparisons and Multiplicity

There is no adjustment for multiplicity in primary or secondary analyses.

5.6. Other Considerations for Data Analyses and Data Handling Conventions

Other considerations for data analyses and data handling conventions are outlined in the following appendices:

Section	Component
15.3	Appendix 3: Assessment Windows

Section	Component
15.4	Appendix 4Study Phases
15.5	Appendix 5: Data Display Standards & Handling Conventions
15.6	Appendix 6: Derived and Transformed Data
15.7	Appendix 7Reporting Standards for Missing Data
15.8	Appendix 8Values of Potential Clinical Importance

6. STUDY POPULATION ANALYSES

6.1. Overview of Planned Analyses

The study population analyses will be based on the All Treated population, unless otherwise specified.

Study population analyses including analyses of participant's disposition, protocol deviations, demographic and baseline characteristics, prior and concomitant medications, exposure and treatment compliance, disease characteristics at initial diagnosis and at screening, prior and follow-up anti-cancer therapy, and substance use will be based on GSK Core Data Standards. Details of the planned displays are presented in Appendix 12Only primary and secondary endpoints will be described in this analysis plan and necessarily conducted for the final clinical and statistical report.

6.2. Disposition of Subjects

A summary of the number of subjects in each of the analysis populations described in Section 4 will be provided. In addition, the number of subjects enrolled will be summarized by country and by center. In addition, a listing of subjects excluded from any analysis population will also be provided.

A summary and listing of screening status and reasons for screen failure will be provided using the Screened population.

A summary of subject status and reason for study withdrawal will be provided. This display will show the number and percentage of subjects who completed the study, are ongoing as of the analysis cutoff date, or withdrew from the study, including primary reasons for study withdrawal. Reasons for study withdrawal will be presented in the order they are displayed in the eCRF. A listing will also be provided.

A summary of study treatment status will be provided. This display will show the number and percentage of subjects who are ongoing or have discontinued study treatment and a summary of the primary reasons for discontinuation of study treatment. Reasons for study treatment discontinuation will be presented in the order they are displayed in the eCRF. A listing of study treatment discontinuation will be generated. The listing will include last dose date, and reasons for study treatment discontinuation.

6.3. Protocol Deviations

Refer to Section 4.2 for the details.

6.4. Demographic and Baseline Characteristics

The demographic characteristics (e.g., age, race, ethnicity, sex, baseline height, and baseline body weight, BMI) will be summarized and listed. Age, height and weight will be summarized using the mean, standard deviation, minimum, median, and maximum. In addition, age will also be categorized and summarized by 18-64, 65-74, and >74. In a separate summary, age will be categorized as 12-17, 18-64, 65-84, >=85 using EudraCT standard. The count and percentage will be computed for sex and ethnicity. Race and racial combinations will be summarized and subject-level race detail will be listed.

6.5. Concomitant Medications and Medical Conditions

Concomitant medications will be coded using GSK drug coding dictionary and listed.

Note: To be considered concomitant, the medication must have been taken at some point during the on-therapy window. Please refer to Appendix 4for the details of concomitant medications classification.

Past and current medical conditions will be summarized in separate tables.

6.6. Anti-Cancer Therapy

Prior anticancer therapy will be coded using GSK Drug coding dictionary and will be classified by type (chemotherapy, immunotherapy, hormonal therapy, biologic therapy, small molecule targeted therapy, and vaccine, etc.). Some prior anticancer therapy may not have type available and will be summarized under "Other". A summary for only those marked "Advanced or Metastatic" will also be produced. Prior anticancer therapy will also be listed.

The number and percentage of subjects that received chemotherapy, immunotherapy, hormonal therapy, biologic therapy, radioactive therapy, small molecule targeted therapy, as post study treatment anti-cancer therapy will be summarized. Time from study treatment discontinuation to the first post study treatment anti-cancer therapy will also be included in this summary table. Surgeries and radiotherapies will be added to this follow-up table. A listing of the type of follow-up anti-cancer therapy received (chemotherapy, immunotherapy, hormonal therapy, biologic therapy, radioactive therapy, small molecule targeted therapy) for each subject will be provided for ACC patients only.

Anatomical Therapeutic Chemical (ATC) classification Level 1 (Body System) information will be included in the dataset created but will not appear on the listing or summary. Prior and on-treatment cancer and non-cancer related surgeries will be listed.

6.7. Disease Characteristics

Disease history and characteristics (time since initial diagnosis in months, stage at initial diagnosis, etc.) at screening will be listed. Separate summaries of disease characteristics at initial diagnosis and screening will be provided.

6.8. Treatment Compliance

Compliance will not be reported. However, summaries of study treatment exposure and dose modifications (e.g., duration of treatment in months, number of dose reductions, number of dose interruptions, number of dose escalations) will characterize exposure. These analyses are described in Section 8.1 'Extent of Exposure'.

7. EFFICACY ANALYSES

All efficacy analyses will be based on the All Treated Population unless otherwise specified. Details of data displays are presented in Appendix 12: List of Data Displays.

Lesion assessment method and timing, evaluation of disease, disease progression and response criteria will be conducted according to RECIST 1.1 for subjects with solid tumors [Eisenhauer, 2009], standardized Response Assessment in Neuro-Oncology (RANO) [Wen, 2010] for subjects with GBM, and Lugano criteria for subjects with NHL [Cheson, 2007; Cheson, 2014]. In addition, Part 3 subjects will be assessed according to immune-based RECIST (iRECIST) [Seymour, 2017]. The timepoint overall response is accessed by the investigator and recorded on the eCRF.

The following table outlines the response criteria by cohorts or treatment group.

Table 8 Response Criteria by Cohort/Treatment Group

Cohort/Treatment Group	Response Criteria	Primary Assessments by	
Part 1 and Part 2, Subjects with solid tumors	RECIST 1.1	Investigator	
Part 2, GBM Cohort	RANO	Investigator	
Part 2, NHL Cohort	Lugano	Investigator	
Part 3 Subjects	iRECIST	Investigator	

Abbreviation: RANO = Response Assessment for Neuro-Oncology; RECIST = Response Evaluation Criteria in Solid Tumors; GBM= Glioblastoma multiforme; NHL = Non-Hodgkin's lymphoma.

7.1. Primary Efficacy Analyses

7.1.1. Confirmed Overall Response Rate (ORR) based on RECIST 1.1 for Part 2 (non-GBM, non-NHL) cohorts

The primary endpoint for all Part 2 cohorts, except GBM, will be overall response rate (ORR). The timepoint overall response is assessed by the investigator and recorded on the eCRF. The ORR endpoint is defined as % of subjects achieving a best response of CR and PR recorded from the start of treatment until disease progression or start of new anti-cancer therapy, whichever is earlier.

Best response will be determined programmatically based on investigator assessment at each time point. If there are two assessments, separated by not evaluable (NE) assessment(s), the best response shall be assessed applying the algorithm below, collapsing data by ignoring NE assessments. The first assessment may occur before the first planned assessment.

Confirmed responses, as outlined in RECIST 1.1 [Eisenhauer, 2009] will be summarized, as appropriate. Confirmation of response may be based on planned and/or unscheduled assessments.

The confirmed overall response rate (ORR) is defined as the ORR as per disease-specific criteria (more details in protocol Section 14.4). Subjects with unknown or missing response will be treated as non-responders, i.e., these subjects will be included in the denominator when calculating the percentage. The best overall response is a subject's best response over the time period referenced. In addition, with respect to best response:

- To be assigned a status of SD, follow-up disease assessment must have met the SD criteria at least once after the first dose for a minimum of 49 days.
- If the minimum time for SD is not met, best response will depend on the subsequent assessments. For example, if an assessment of PD follows the assessment of SD and SD does not meet the minimum time requirement the best response will be PD. Alternatively, subjects lost to follow-up after an SD assessment, not meeting the minimum time criteria, will be considered not evaluable.
- To be assigned a status of PR or CR, a confirmatory disease assessment should be performed no less than 4 weeks (28 days) after the criteria for response are first met.

The ORR will be summarized with a 2-sided 95% exact confidence interval based on the Clopper-Pearson method. The observed confirmed ORR will be reported at the interim and final analysis and will be summarized by cohort.

7.1.2. Overall Response Rate (ORR) based on Lugano for Part 2 NHL Cohorts

Overall response confirmation is not needed for assessment according to Lugano criteria [Cheson, 2007; Cheson, 2014]. The NHL cohort will only have ORR summarized. Timepoint response will be the combined imaging response based on both anatomic and metabolic responses according to the following table:

Anatomic/Radiologic Response	Metabolic Response	Combined Imaging Response	
CR	CMR, NE, missing	CR	
PR	CMR	CR	
CR	PMR	PR	
CR	NMR, SMD	PR	
PR	PMR	PR	
PR	NMR, SMD	PR	
SD	PMR	PR	
PD	PMR	PD	
SD	NMR, SMD	SD	
CR, PR, SD or NE	PMD	PD	

Table 9 Overall Response Rate

Anatomic/Radiologic Response	Metabolic Response	Combined Imaging Response
CR, PR, SD or NE	NE, missing	CR, PR, SD or NE (Anatomic Response)
PD	NMR, SMD	PD
PD	PMD	PD
PD	NE, missing	PD

CR = complete response; NE = not evaluable; PR = partial response; PD = unconfirmed progressive disease; SD = stable disease; SMD = No Metabolic Response.

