To evaluate the preliminary effects of fed versus fasted administration on the pharmacokinetics of GSK3326595	GSK3326595 PK parameters in plasma following single-dose administration of GSK3326595 in a fed or fasted state
 To evaluate the relative bioavailability of GSK3326595 tablets as compared to capsules 	GSK3326595 PK parameters in plasma following single-dose administration of GSK3326595 in tablet or capsule formulation
Exploratory	

Part 2 (Dose Expansion)				
Objectives	Endpoints			
Primary				
To determine clinical activity of GSK3326595 in disease-specific expansion cohorts	 Solid tumor (non-glioblastoma multiforme, GBM) cohorts: Overall response rate (ORR, defined as % of subjects achieving CR and PR) based on RECIST 1.1 criteria GBM cohort: Six-month progression free survival (PFS) rate, defined as the percentage of subjects free from radiographic progression per Response Assessment in Neuro-Oncology (RANO) criteria, or death due to any cause, for six months after starting GSK3326595. Non-Hodgkin's lymphoma cohort(s): ORR (% of subjects achieving CR and PR) based on Lugano criteria 			
Secondary				
 To further describe the clinical activity of GSK3326595 	 PFS, defined as time from first dose until radiographic progression per standard criteria, or death due to any cause, whichever is earlier. 			
	 GBM cohort: Overall Response Rate (CR + PR) based on RANO Working Group criteria 			
	 ACC tablet cohort: Duration of response (DOR), defined as time from first evidence of response (CR or PR per RECIST 1.1) to earlier date of disease progression or death due to any cause, as determined by Investigator assessment 			
	 ACC tablet cohort: Overall survival (OS), defined as time from first dose until death from any cause in ACC subjects who are systemic-treatment naïve 			
 To evaluate the safety and tolerability of GSK3326595 in subjects treated at the RP2D 	 AEs, SAEs, dose reductions or delays, withdrawals due to toxicities and changes in safety assessments (e.g., clinical laboratory parameters, vital signs, physical examinations, and organ-specific parameters). 			
Exploratory				

Part 2 (Dose Expansion)		
Objectives	Endpoints	
CCI		

Part 3 (Combination with Pembrolizumab)			
Objectives	Endpoints		
Primary			

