Decisions are based on whether the posterior probability that the ORR exceeds its corresponding historical control is sufficiently low compared to fixed statistical thresholds. If this posterior probability is sufficiently low within a given cohort (≤ 0.15), then enrollment may be halted early for futility. At the final analysis and after the study has been closed, if the posterior probability is sufficiently high (≥ 0.87), then the dose will be declared efficacious for that cohort. Separate from model estimates, the observed ORR will also be reported for each cohort.

Enrollment into each disease-specific cohort will continue during the conduct of each interim analysis subsequent to the decision of whether or not to declare futility. The total number may be increased up to a total of 32 evaluable subjects for the TNBC cohort, up to a total of 25 evaluable subjects for each of the two NHL cohorts, and up to 40 evaluable subjects for the mTCC cohort, depending on the results observed; a separate decision will be made for each disease cohort. Enrollment into each tumor specific cohorts can only be terminated for futility (i.e., lack of clinical activity), notwithstanding the provisions of Section 5.5; otherwise enrollment will continue to the planned maximum sample size in each cohort. Inference stemming from the Bayesian hierarchical model of GSK3326595 efficacy in subjects harboring these four tumor types are intended to inform decision making. Actual decisions will depend on the totality of the data.

Subjects enrolled in Part 1 may be included in the Part 2 efficacy analysis provided that they were treated at the RP2D and have a disease under study in Part 2.

The decision to terminate a disease-specific cohort will not depend solely on the results of the statistical model but will take all factors into account, including the results of the model, safety, tolerability, PK, and PD data. In some cases (e.g., under-representation of a given predictive biomarker in the subjects treated at the time of interim analysis), additional subjects in a cohort may be enrolled even if the model suggests a low likelihood of activity in that tumor type.

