- 19. CR or PR should be confirmed not earlier than 28 days from the initial response scan, as per international working group criteria; see Section 14.4.3
- 20. Survival Follow-Up via telephone, email or other form of communication, every 6 months. Following Protocol Amendment 7, survival follow-up should only be conducted for subjects in an ACC cohort. Follow-up will continue until approximately 70% of subjects in the ACC cohorts have died.

See Section 5.4 for further details

Table 15 Time and Events for Part 3 (Active in all regions, except France)

Procedure	Screening		Da	ys 1-35		q3w	q8w	q26w	EOT (within
		Day 1	Day 8	Day 15	Day 22	(starting W6)	(starting W8)	(starting W26)	30 days post-
Screening		l				110,	110/	1120/	1401 4000)
Informed consent	Х								
Demography	Х								
Medical History	Х								
Inclusion/Exclusion Criteria	Х								
Disease Characteristics	Х								
Prior Therapy	Х								
Register Subject	Х								
Safety	•								
Full Physical Examination ¹	Х								Х

TMF-14123404

CONFIDENTIAL

204653

Procedure	Screening		Day	/s 1-35		q3w	q8w	q26w	EOT (within
Limited Physical Examination ¹	-	Х	Х	Х	Х	X	·	·	
ECOG Performance Status ²	Х	Х	Х	Х	Х	Х			Х
Vital Signs	Х	Х	Х	Х	Х	Х			Х
12-lead ECG	Х	PK ³		PK ³			Х		Х
DEXA Bone Densitometry	X4						Х		X ⁵
Pregnancy test (Females of childbearing potential only; screening test must be within 7 days prior to first dose)	х				Х	Х			Х
FSH/Estradiol (Only in women of non- childbearing potential)	х								
HIV, HbsAg, HCV Antibody Screening ⁶	Х								
Routine Clinical Laboratory Assessments ⁷	Х	Х	Х	Х	Х	Х			Х
Folate and selected vitamins ⁷	Х				Х		Х		Х
Ophthalmic Assessment ⁸	Х							Х	Х
Study Treatment									
Administer GSK33265959			←=====		==Daily Dosing=	===========	====→		
Administer Pembrolizumab				Х		Х			
Vision Symptom Review ¹⁰	Х	Х	Х	Х	Х	Х			Х
AE Review			Co	ntinuous from the	start of study tre	atment until th	e follow-up co	ntact	
SAE Review			Continuous	from signing of in	formed consent	until the follow	-up contact		
Concomitant Medication Review				Continuous from	signing of infor	med consent			
Pharmacokinetics (PK), Pharmacodynami	cs (PD) & Pharr	nacogenomics	s (PGx)						
PK Plasma ¹¹		Х		Х			Х		
Pembrolizumab PK ¹²				Х	Х	X (Q6W starting W6)			х
Pembrolizumab Immunogenicity ¹³				Х		X (Q6W starting			Х

TMF-14123404

CONFIDENTIAL

Procedure	Screening		Day	ys 1-35	q3w	q8w	q26w	EOT (within
					W6)			
Tumor Biopsy (archival) for p53 status	Х							

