11.9.6. Interim Futility Analysis

Interim data will be evaluated to monitor efficacy and safety. For the GBM cohort, a planned interim analysis for futility will be performed when at least 10 evaluable subjects have been enrolled in this expansion cohort. Enrollment may be stopped early for toxicity or lack of efficacy, should various criteria occur based on accrued data. The design criterion for early stop for futility based on Bayesian Predictive Adaptive Design is described in Section 11.3. For TNBC, mTCC, and NHL cohorts, the decision criteria for early stop for futility based on Bayesian Hierarchical model are described below. The decision will be made for each individual disease-specific cohort. For the ACC capsule cohort, one interim futility analysis will be performed when first treated 10 subjects become evaluable. If there are 1 or fewer responders in these 10 subjects, the cohort will be stopped early for futility. For the ACC tablet cohort, one interim futility analysis will be performed when the first 17 treated subjects become evaluable. If there are 2 or fewer responders in these 17 subjects, the cohort will be stopped early for futility. This rule is intended as a guideline, development decisions will depend on the totality of the data. For ER+BC cohort, the first interim analysis will be conducted when at least 10 subjects become evaluable. The details about interim decision rules are specified in Section 11.6. For HPV+ cohort, the first interim analysis will be conducted when at least 10 subjects become evaluable. The details about interim decision rules are specified in Section 11.7.
For the NSCLC cohort, one interim futility analysis will be performed when first treated 10 p53 wild-type subjects become evaluable. If there are 1 or fewer responders in these 10 subjects, the cohort will be stopped early for futility.

For TNBC, mTCC, and NHL cohorts, the therapeutic effect will be declared insufficient, and termination of enrollment will be recommended, if a minimum of 10 subjects become evaluable and the posterior probability that the confirmed ORR is greater than its corresponding historical control (C_j) is sufficiently low (<15%) based on the hierarchical model. That is,

P ($\pi_j > C_j$ | current data) < 15%, for the j-th cohort, j=1,..4

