11.10.2.3. Efficacy Analysis

The confirmed overall response rate (ORR) is defined as the percentage of subjects with a confirmed complete response (CR) or a partial response (PR) at any time as per disease-specific criteria (Section 14.4). Subjects with unknown or missing response will be treated as non-responders, i.e. these subjects will be included in the denominator when calculating the percentage. Exact methods for calculated confidence intervals will be given in the RAP.

The number and types of responses, as outlined in RECIST 1.1 (for subjects with solid tumors), RANO (for subjects with GBM), and Lugano (for subjects with NHL), will be listed and summarized separately, as appropriate.

The observed confirmed ORR will be reported at the interim and final analysis for each cohort specified in Part 2 treated at RP2D. The estimates along with 95% confidence interval (CI) based on a normal approximation will be provided. Bayesian inference based on summary statistics from the posterior distributions of each ORR will be reported at interim and final analyses. The posterior mean and posterior 2.5% and 97.5% percentiles of the ORR will be calculated for each cohort. In addition, the posterior probability that the ORR exceeds its corresponding historical control will be reported for each cohort.

Progression-free survival rate (PFSR) is calculated from the start of treatment until the date of progression or death from any cause. The PFSRs at 6 months were estimated by the Kaplan-Meier method. These rates estimated the proportion of patients who did not progress and were alive at month 6. The 95% confidence intervals for the PFSR at month 6 will be estimated using Greenwood's estimate of the standard error (SE) and a linear transformation of the progression-free survival function.

Duration of response is defined as the time from first documented evidence of CR or PR until the first documented sign of disease progression or death, for the subset of subjects with a confirmed CR or PR. Duration of response will be summarized descriptively for each cohort, if data warrant, using Kaplan-Meier medians and quartiles. Details on rules for censoring will be provided in the RAP.

For the ACC tablet cohort, duration of response will be analyzed as determined by the Investigator assessment.

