2. SUMMARY OF KEY PROTOCOL INFORMATION

2.1. Changes to the Protocol-Defined Statistical Analysis Plan

There were no changes or deviations to the originally planned statistical analysis specified in the protocol amendment 8 (dated: 20/APR/2022).

Section 2.2 replicates what is in protocol amendment 8 (dated 20 April 2022).

In general, the plan will be to report all the primary and secondary outcomes, and none of the exploratory outcomes (including pharmacodynamics and genetics outcomes). The following is the exception to this plan:

- Additional secondary analyses, for Part 1 are investigator-assessed percent change from baseline, and maximum percent reduction from baseline in sum of diameters, and progression-free survival (PFS), defined as time from first dose until radiographic progression per standard criteria, or death due to any cause, whichever is earlier.
- All Part 2 ACC cohorts will be included in the overall survival analysis.
- Time to response listings will be included with duration of response analyses for ACC TN cohort.
- All NHL P53 cohorts are being compared as part of secondary analyses, not exploratory analyses.
- PK analyses are considered secondary.
- Progression free survival (PFS) rate at six months after starting GSK3326595 will be conducted as a secondary analysis for all Part 2 cohorts not including GBM (for which this is the primary analysis).
- Progression free survival (PFS) rate at six months after starting GSK3326595 will be estimated using Kaplan-Meier plots (only) as a secondary analysis for Part 1 and Part 3 cohorts.

White blood cells will be included with laboratory assessments summarized. (Section 8.4.2)

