15.12.5. Efficacy Tables

		IDSL / Example			
No.	Population	Shell	Title	Programming Notes	Deliverable
Tumor	Response		•		
2.1	All Treated	RE1a	Summary of Investigator Assessed Best Response with Confirmation (RECIST 1.1 Criteria)	By dose level for Part 1, by cohort for Part 2 (all but NHL/GBM) 95% CI is based on Clopper-Pearson exact CI	IA, SAC
2.2	All Treated	RE1a	Summary of Investigator Assessed Best Response with Confirmation (RANO Criteria)	Part 2 GBM cohort 95% CI is based on Clopper-Pearson exact CI	SAC
2.3	All Treated	RE1a	Summary of Investigator Assessed Best Response (Lugano Criteria)	Part 2 NHL cohort 95% CI is based on Clopper-Pearson exact Cl	IA, SAC
2.4	All Treated	RE1a	Summary of Investigator Assessed Best Response with Confirmation (iRECIST Criteria)	Part 3 by dose level 95% CI is based on Clopper-Pearson exact CI	SAC
Time-te	o-Event				
2.5	All Treated	TTE6	Summary of Kaplan-Meier Estimates of Progression-Free Survival at 6 Months (RANO Criteria)	GBM cohort	IA, SAC
2.6	All Treated	TTE1	Summary of Progression-Free Survival Based on Investigator Assessments (RECIST 1.1 Criteria)	By cohort for Part 2 (excluding GBM, NHL)	SAC
2.7	All Treated	TTE1	Summary of Progression-Free Survival Based on Investigator Assessments (RANO Criteria)	GBM cohort	SAC
2.8	All Treated	TTE1	Summary of Progression-Free Survival Based on Investigator Assessments (Lugano Criteria)	NHL cohorts	SAC
2.9	All Treated	TTE1a	Summary of Duration of Response Based on Investigator Assessments (RECIST 1.1 Criteria)	Part 2 ACC TN cohort	SAC

204653

		IDSL / Example			
No.	Population	Shell	Title	Programming Notes	Deliverable
2.10	All Treated	TTE1	Summary of Overall Survival	Part 2 ACC TN cohort and all ACC subjects across parts 1/2	SAC

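### The SAP scores NHL response without confirmation, so the confirmed NHL ORR stated in protocol 11.10.2.3 is not produced, and SAP 2.1 does not declare the difference

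*SAP*

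**What the plan says.** Three protocol places use confirmed response for NHL.

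- Section 11.9.6, in the paragraph on TNBC, mTCC and NHL, bases the futility rule on "the posterior probability that the confirmed ORR is greater than its corresponding historical control".
- Section 11.10.2.3 says "The observed confirmed ORR will be reported at the interim and final analysis for each cohort specified in Part 2", with no exception for NHL.
- Table 14 note 19, attached to the NHL disease-assessment row, says "CR or PR should be confirmed not earlier than 28 days from the initial response scan, as per international working group criteria" and points to section 14.4.3.

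Other protocol places do not. The NHL primary endpoint is "ORR (% of subjects achieving CR and PR) based on Lugano criteria". The decision thresholds in 4.3.3.2 (0.15 and 0.87) refer to "the posterior probability that the ORR exceeds its corresponding historical control". Sections 8.7.3 and 14.4.3 contain no confirmation rule.

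SAP 7.1.2 states "Overall response confirmation is not needed for assessment according to Lugano criteria". The planned display is Table 2.3, "Summary of Investigator Assessed Best Response (Lugano Criteria"), whereas the titles of Tables 2.1, 2.2 and 2.4 all specify confirmation. Listing 45 differs from Listings 43, 44 and 46 in the same way, and SAP 3.1.9 makes the same split for the publication interim. SAP 2.1 opens with "There were no changes or deviations to the originally planned statistical analysis specified in the protocol amendment 8" and then lists exceptions. NHL confirmation is not among them.

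**The concern.** The definition of response for a primary endpoint differs between the SAP and the protocol's own efficacy-analysis section, and the section of the SAP meant to record such differences is silent. A reader of the final report who relies on SAP 2.1 would take the NHL ORR to be the confirmed rate described in 11.10.2.3. It will be the unconfirmed rate, which within any cohort can only be equal or higher, because confirmed responders are a subset of all responders.

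The rate is read against a 10% control and a 30% target (protocol 11.1, SAP 2.4). If the control is a confirmed rate, an unconfirmed numerator is too generous. If it is an unconfirmed rate, the SAP's scoring is the matching one. The documents do not say which applies.

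**Working it through.** **Passages compared**

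| Place | NHL response |
|---|---|
| Protocol 11.9.6, futility rule | Confirmed; NHL named |
| Protocol 11.10.2.3, reported ORR | Confirmed; each Part 2 cohort |
| Protocol Table 14 note 19 | Confirm at 28 days or later |
| Protocol synopsis and section 3 endpoint | Confirmation not mentioned |
| Protocol 4.3.3.2, 0.15 and 0.87 rules | Confirmation not mentioned |
| Protocol 8.7.3 and 14.4.3 | No confirmation rule |
| SAP 7.1.2, Table 2.3, Listing 45 | Unconfirmed |
| SAP 2.1 | Not listed as a change |

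**Step 1: effect of one response.** The maximum per NHL cohort is 25 evaluable subjects (protocol 4.3.3.2). One response is 1/25 = 4 percentage points. SAP Table 2.3 uses Clopper-Pearson limits: lower = Beta quantile(0.025; x, n − x + 1), upper = Beta quantile(0.975; x + 1, n − x).

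- x = 6, n = 25: 24%, 95% CI 9.4 to 45.1
- x = 7, n = 25: 28%, 95% CI 12.1 to 49.4

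Between 6 and 7 responders the interval moves from including 10% to excluding it. This needs no assumed confirmation rate. It describes the reported interval; it is not a decision rule in either document.

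**Step 2: can Table 21 settle the scale?** Re-simulating the Appendix 11 clustered model gave NHL power of 0.94 to 0.96 in the All Positive scenario (Table 21: 0.95 and 0.96). The All Null error rate was 0.06 to 0.08 (Table 21: 0.06 and 0.05). Power reproduces; the error rate is close but not exact. Table 21 labels its rates neither confirmed nor unconfirmed, so it cannot say what the 10% means.

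**Step 3: why the direction is open (illustration only).** Let k be the share of first responses that would confirm. The documents give no value; k = 0.9, 0.8 and 0.7 are assumed. As a simple stand-in for the hierarchical model, take one cohort of 25 with the weak prior Beta(0.03, 0.07), which the protocol uses for its GBM and HPV+ cohorts. Requiring P(ORR > 10%) ≥ 0.87 then means at least 5 responders in 25.

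- Control is a confirmed rate and unconfirmed responses are counted. The null rate becomes 0.10/k, and P(X ≥ 5) rises from 0.098 (k = 1) to 0.137, 0.195 and 0.281.
- Control and target are unconfirmed rates and confirmed responses are counted. The target rate becomes 0.30 × k, and power falls from 0.910 to 0.845, 0.752 and 0.627. Counting unconfirmed responses here causes no inflation.

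The two cases point in opposite directions, and the documents do not choose between them.

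**Step 4: can a confirmed rate be derived?** Scheduled NHL scans are 12 weeks (84 days) apart, and 24 weeks (168 days) apart after week 48 (protocol 8.2.2). Any later scheduled scan therefore meets the 28-day minimum, and the confirmed rate can be derived from data already collected.

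**The case against.** The strongest case for the SAP is that it applies the protocol rather than departing from it. Section 11.10.2.3 defines confirmed ORR by the disease-specific criteria in 14.4. That section states a confirmation requirement for RECIST and for RANO, and none for Lugano. Section 8.7 shows the same contrast: 8.7.1 and 8.7.4 specify confirmed responses and 8.7.3 does not. SAP 7.1.1 also defines confirmed ORR by reference to 14.4. The choice is openly stated in 7.1.2, the table titles and 3.1.9.

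Much of this stands. A reader might infer that SAP 7.1.2 contradicts the NHL primary endpoint, but the endpoint wording never says confirmed. The argument does not account for 11.9.6, which attaches confirmation to a rule covering NHL, or for note 19, which asks for confirmation on the NHL row. Choosing between conflicting passages is legitimate; leaving the choice out of SAP 2.1 is the gap.

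A reader might also infer that unconfirmed scoring inflates the false-positive rate. That needs a confirmed-scale control. The comparison in 11.9.6 hints at one but does not state it, and the endpoint wording points the other way. Nor does any passage send the 7.1.2 responses into the hierarchical model. SAP 3.1.2 takes its thresholds from the protocol without saying which NHL responses are used, and SAP 1 places that analysis outside the work of the group executing the rest of the SAP.

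**Conclusion.** The point holds as an undeclared difference in how NHL response is defined, with a protocol-stated quantity left unreported. SAP 7.1.2 is a defensible primary definition. What is missing is the declaration in SAP 2.1, the confirmed NHL ORR of 11.10.2.3, and the scale of the 10% and 30% rates.

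The established size is 4 percentage points of reported ORR per unconfirmed response at 25 subjects. How many such responses there are is not known from the documents. The error-rate figures in the working rest on assumed confirmation shares and a simplified single-cohort rule; they show only that the sign of any bias depends on an unstated fact. Recruitment has stopped, so no futility decision remains, and 4.3.3.2 says the model informs decisions rather than fixing them. The consequence is confined to the final NHL result and its interpretation. It should be corrected.

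**What to change.** 1. In SAP 2.1, declare that the NHL primary ORR is unconfirmed per Lugano and differs from the confirmed-ORR wording of protocol 11.10.2.3, 11.9.6 and Table 14 note 19.
2. Keep 7.1.2 as the primary definition. The study is open-label and protocol 4.3.1 shows NHL responses had been reviewed by December 2019, so choosing the primary scale now could be driven by the data. Add to Table 2.3, as a sensitivity analysis, the confirmed NHL ORR (repeat assessment at 28 days or later) with its exact CI, and the number of first responses with no later assessment.
3. State whether the 10% and 30% rates are confirmed or unconfirmed, or say that this is unknown. State which NHL responses enter the final 0.87 rule.

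No protocol amendment and no change to the futility rule are needed. The cost is one derived variable, one extra column and one count in Table 2.3, and a few sentences in the SAP. The confirmed estimate may be lower. Some late responses cannot be confirmed, because scans are 12 to 24 weeks apart and efficacy assessments end with Amendment 8 (protocol 8.7). The count of first responses without a later assessment makes that visible.
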